3. STUDY DESIGN

The design is a two-arm, parallel-assignment randomized controlled trial design to test the efficacy of iCBT ESTEEM compared to self-monitoring control. The unit of randomization is the individual. The primary outcome is number of past-30-day CAS with primary or casual partners at 8-mo follow-up, assessed via Timeline Follow-Back. A total of 120 YMSM participants were enrolled in the study ($n = 60$ per condition).

STATISTICAL ANALYSIS PLAN

4. OUTCOMES

The primary and secondary outcome measures, each measured via self-report at baseline, immediate post-intervention (4-month follow-up), and 8-month follow-up (with the exception of HIV/STI testing results, which were measured via testing kits at baseline and 8-month follow-up), are summarized in Table 1.

Table 1. Primary (1'), Secondary (2'), and Exploratory (3') Outcome Measures		
Domain	Measure (1°, 2°, 3°)	Source
HIV-risk behavior	Condomless anal sex with primary or casual partners (1°; 2°)	Past 30-Day Timeline Follow-Back
	Condomless anal sex with casual partners only (2°)	Past 30-Day Timeline Follow-Back
	Safer sex self-efficacy (2°)	Safer Sex Questionnaire (SSQ)
	Decisional balance (2°)	Decisional Balance for Condom Use Scale (DBCUS)
	HIV/STI testing history (2')	Past 4-month HIV/STI Testing Questionnaire
	HIV/STI testing results (2')	Rapid testing kits for HIV and syphilis
Mental health and substance use	Depression symptoms (2°)	Patient Health Questionnaire-9 (PHQ-9)
	Depression severity and impairment (3')	Overall Depression Severity & Impairment Scale (ODSIS)
	Anxiety symptoms (2°)	Generalized Anxiety Disorder-7 (GAD-7)
	Anxiety severity and impairment (3')	Overall Anxiety Severity & Impairment Scale (OASIS)
	Alcohol and substance use (2°)	Alcohol Use Disorders Identification Test (AUDIT), Drug Use Disorders Identification Test (DUDIT)
	Suicidality (2°)	Suicidal Ideation Attributes Scale (SIDAS)
Minority Stress	Concealment motivation (2°)	Lesbian, Gay, and Bisexual Identity Scale (LGBIS) Concealment Motivation subscale
	Acceptance concerns (2°)	LGBIS Acceptance Concerns subscale
	Internalized Homonegativity (2°)	LGBIS Internalized Homonegativity subscale
	Self-esteem (3')	Rosenberg Self-Esteem Scale (RSE)

STATISTICAL ANALYSIS PLAN

Universal Stress processes	Emotional Regulation (2°)	Difficulties in Emotion Regulation Scale-Short Form (DERS)
	Rumination (2°)	Ruminative Response Scale (RRS)
	Social Support (2°)	Multidimensional Scale of Perceived Social Support (MSPSS), LGBIS - LGB-Specific Family Support subscale

4.1 Primary Outcome

The primary outcome is past-30-day condomless anal sex with main or casual partners at 8-month follow-up assessed via Timeline Follow-Back.

4.2 Secondary Outcomes

HIV/STI risk behaviors:

- *Condomless anal sex with primary or casual partners* – Timeline Follow-Back (4-mo)
- *Condomless anal sex with casual partners* – Timeline Follow-Back (4- and 8-mo)
- *Safer sex self-efficacy* – Safer Sex Questionnaire (4- and 8-mo)
- *Decisional balance for condom use* – Decisional Balance for Condom Use Scale (4- and 8-mo)
- *HIV/STI testing history* – Past 4-month HIV/STI Testing Questionnaire (4- and 8-mo)
- *HIV/STI test results* – Rapid testing kits for HIV and syphilis (8-mo follow-up only)

Mental health outcomes:

- *Depressive symptoms* – Patient Health Questionnaire-9 (4- and 8-mo)
- *Anxiety symptoms* – Generalized Anxiety Disorder-7 (4- and 8-mo)
- *Suicidal ideation* – Suicidal Ideation Attributes Scale (4- and 8-mo)
- *Alcohol and substance use* – Alcohol Use Disorders Identification Test, Drug Use Disorders Identification Test (4- and 8-mo)

Minority stress mechanism outcomes:

- *Concealment motivation* – Lesbian, Gay, and Bisexual Identity Scale (LGBIS) Concealment Motivation subscale (4- and 8-mo)
- *Acceptance concerns* – LGBIS Acceptance Concerns subscale (4- and 8-mo)
- *Internalized homonegativity* - LGBIS Internalized Homonegativity subscale (4- and 8-mo)

Universal mechanism outcomes:

- *Emotion regulation* – Difficulties in Emotion Regulation Scale-Short Form (4- and 8-mo)

STATISTICAL ANALYSIS PLAN

- *Perceived social support* – Multidimensional Scale of Perceived Social Support, Chinese version of the LGBIS - LGB-Specific Family Support subscale (4- and 8-mo)
- *Rumination* – Ruminative Response Scale (4- and 8-mo)

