4.2 Outcome Variables/Endpoints

Our primary outcome is YMSM's sexual health and HIV risk behavior, which will be assessed at three study time points (baseline, 4-month follow-up, 8-month follow-up) via the following measures:

- 30-Day Timeline Follow-Back

- Decisional Balance for Condom Use Scale
- Safer Sex Questionnaire
- Past 4-month HIV/STI Testing Questionnaire

Our secondary outcomes, which will also be measured at baseline, 4-month follow-up, 8-month follow-up, (unless otherwise noted) include the following with their associated measures:

Mental health outcomes:

- *Depressive symptoms* – Patient Health Questionnaire-9, Overall Depression Severity & Impairment Scale
- *Anxiety symptoms* – Generalized Anxiety Disorder-7, Overall Anxiety Severity & Impairment Scale; Social Interaction Anxiety Scale
- *Suicidal ideation* – Suicidal Ideation Attributes Scale
- *Alcohol and substance use* – Alcohol Use Disorders Identification Test, Drug Use Disorders Identification Test

Minority stress mechanism outcomes:

- *Concealment motivation* – Lesbian, Gay, and Bisexual Identity Scale (LGBIS) Concealment Motivation subscale
- *Acceptance concerns* – LGBIS Acceptance Concerns subscale
- *Internalized homonegativity* - LGBIS Internalized Homonegativity subscale
- *Self-esteem* – Rosenberg Self-Esteem Scale

Universal mechanism outcomes:

- *Emotion regulation* – Difficulties in Emotion Regulation Scale-Short Form
- *Perceived social support* – Multidimensional Scale of Perceived Social Support, Chinese version of the LGBIS - LGB-Specific Family Support subscale
- *Rumination* – Ruminative Response Scale

Psychosocial variables:

- *Body image* – Multidimensional Body-Self Relations Questionnaire, Appearance Evaluation subscale, Body Appreciation Scale-2
- *Adverse childhood experiences (ACEs)*; administered at baseline and 8-month follow-up) – Life History Interview of ACEs
- *COVID-19 experiences* (administered at 8-month follow-up) – COVID-19 questionnaire

HIV/STI outcomes (only following video screener and at 8-month follow-up):

- At-home HIV/STI testing kit for HIV and syphilis

In addition to the assessments that will be administered at baseline, 4-month follow-up, and 8-month follow-up, three questionnaires will be administered weekly on the iCBT online platform for 10 weeks for the ESTEEM iCBT and self-monitoring conditions:

- Overall Depression Severity & Impairment Scale
- Overall Anxiety Severity & Impairment Scale

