4.2.2 Secondary and Exploratory Outcome Variables/Endpoints (if applicable)

The following are the secondary outcome variables and associated measures that will be administered at baseline, 4-month follow-up, and 8-month follow-up (unless otherwise noted):

- Mental health outcomes
 - Patient-Health Questionnaire-9 – 10-items from a psychometrically validated measure of depression based on a 4-point Likert scale. The Chinese version of the measure will be used for the present study.
 - Overall Depression Severity & Impairment Scale – 5-items from a measure that has previously been used by the Yale research team to assess changes in depressive symptoms among gay and bisexual men in the US. A translated version of the measure in Chinese will be developed for the present study.
 - Generalized Anxiety Disorder-7 – 8-items from a psychometrically validated measure of depression based on a 4-point Likert scale. The Chinese version of the measure will be used for the present study.
 - Overall Anxiety Severity & Impairment Scale – 5-items from a measure that has previously been used by the Yale research team to assess changes in anxiety symptoms among gay and bisexual men in the US. A translated version of the measure in Chinese will be developed for the present study.

- Social Interaction Anxiety Scale - 20-items that specifically assess symptoms of anxiety in social situation based on a 5-point Likert scale. The Chinese version of the measure will be used for the present study.
- Suicidal Ideation Attributes Scale – 5-items that assess thoughts related to suicide in the past month based on Likert scales from 0 to 10. The Chinese version of the measure will be used for the present study.
- Alcohol Use Disorders Identification Test – 10-items based on eight 4-point Likert scales and two 3-point Likert scales assessing alcohol use behavior. The Chinese version of the measure will be used for the present study.
- Drug Use Disorders Identification Test – 11-items based on nine 4-point Likert scales and two 3-point Likert scales assessing substance use behavior other than alcohol. The Chinese version of the measure will be used for the present study.
- Minority stress mechanism outcomes
 - LGBIS Concealment Motivation subscale – a 3-item subscale from the LGBIS assessing sexual orientation concealment based on a 6-point Likert scale. The Chinese version of the measure's subscale will be used for the present study.

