 - LGBIS Acceptance Concerns subscale – a 3-item subscale from the LGBIS assessing rejection sensitivity based on a 6-point Likert scale. The Chinese version of the measure's subscale will be used for the present study.
 - LGBIS Internalized Homonegativity subscale – a 3-item subscale from the LGBIS assessing internalized homonegativity based on a 6-point Likert scale. The Chinese version of the measure's subscale will be used for the present study.
 - Rosenberg Self-Esteem Scale – 10-items based on a 4-point Likert scale assessing general aspects of self-esteem. The Chinese version of the measure will be used for the present study.
- Universal mechanism outcomes
 - Difficulties in Emotion Regulation Scale-Short Form – 18-items that comprise a total score and six subscales related to emotion (dys)regulation with each item based on a 5-point Likert scale. The Chinese version of the measure will be used for the present study.
 - Multidimensional Scale of Perceived Social Support – 12-items assessing perceived social support from a significant other, family, and friends based on a 7-point Likert scale. A translated version of the measure in Chinese will be developed for the present study.
 - Chinese version of the LGBIS - LGB-Specific Family Support subscale – a 3-item subscale from the LGBIS assessing social support specifically related to family support based on a 6-point Likert scale. The Chinese version of the measure's subscale will be used for the present study.
 - Ruminative Response Scale – 5-items asking individuals to rate on a 4-point Likert-scale how they generally think when feeling down, sad, or depressed. The Chinese version of the measure will be used for the present study.
- Psychosocial variables
 - Multidimensional Body-Self Relations Questionnaire, Appearance Evaluation subscale – 7-items focused on feelings of body (dis)satisfaction with one's physical appearance. All items are based on a 5-point Likert scale. The Chinese version of the measure's subscale will be used for the present study.
 - Body Appreciation Scale-2 – 10-items assessing the level of acceptance people have for their bodies regardless of size or shape, respect and attendance to bodily needs, and protecting the body from internalization of

society's pressure and standards of beauty. All items are based on a 5-point Likert scale. The Chinese version of the measure's subscale will be used for the present study.

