9.6 Study Completion

Data collection for the study will end by November 30, 2022. Data analysis is expected to occur from December 2022 to May 2023. The study is anticipated to be completed by June 1, 2023.

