6.4 Power for Exploratory Outcomes

7 INTERIM MONITORING

7.1 Overview

7.2 Safety

8 ANALYTIC PLAN

8.1 Overview

8.2 Comparability of Treatment Groups

8.3 Analysis of Primary Outcome

8.4 Analysis of Secondary Outcomes

8.5 Qualitative Analyses

8.6 Exploratory Analyses

REFERENCES

STATISTICAL ANALYSIS PLAN

STUDY SUMMARY (revised 1.24.23)

Title	Developing Efficient Intervention Technologies to Reduce Stigma-Related Stress, Mental Health Problems, and HIV Risk among Young Chinese MSM
Study Design	The design is a two-arm, parallel-assignment randomized controlled trial design to test the efficacy of an internet-based cognitive behavioral therapy (iCBT), Effective Skills to Empower Effective Men (ESTEEM), in comparison to self-monitoring control. The unit of randomization is the individual.
Study Duration	2.67 years
Trial Sites	Hunan province, China (Central South University)
Objective	The primary objective is to evaluate the preliminary efficacy of a Chinese-adapted version of iCBT ESTEEM on young men who have sex with men's (YMSM) HIV risk behavior compared to self-monitoring control. Secondary outcomes will include HIV social-cognitive risk factors, HIV/STI test results, mental health, universal psychosocial risk factors for mental and behavioral health problems, and minority stress. The secondary objectives of this study are to determine whether baseline minority stress exposure moderates treatment efficacy, such that participants with the most minority stress exposure benefit more from iCBT ESTEEM than from self-monitoring control.
Number of Subjects	120
Main Inclusion Criteria	
 (1) 16-30 years old (2) Live in Hunan province, China (3) Current gender identity as male (4) Report past 12-month sex with men (5) Be confirmed HIV-negative upon at-home testing (6) Report past 3-month condomless/PrEP-less anal sex (7) Past-week symptoms of depression or anxiety using the Brief Symptom Inventory-4, cutoff of 2.5 on either the depression subscale, anxiety subscale, or both (8) No past 3-month mental health services of more than 2 visits per month (9) Weekly access to internet on a laptop, desktop, or tablet device (10) Ability to read, write, and speak in Mandarin (11) Provision of informed consent

STATISTICAL ANALYSIS PLAN

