4.3 Exploratory Outcomes

- *Depression severity and impairment* -- Overall Depression Severity and Impairment Scale (4- and 8-mo)
- *Anxiety severity and impairment* – Overall Anxiety Severity and Impairment Scale (4- and 8-mo)
- *Self-esteem* – Rosenberg Self-Esteem Scale (4- and 8-mo)

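### Three scales that the protocol lists as secondary, chiefly the Social Interaction Anxiety Scale, are missing without a reason from a SAP revised after the planned end of data collection

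*SAP*

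**What the plan says.** **Protocol**

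- Section 4.2.2 opens with "The following are the secondary outcome variables and associated measures" and schedules these at baseline, 4 and 8 months unless otherwise noted. The section title allows for exploratory outcomes, but no instrument is labelled exploratory.
- For anxiety, section 4.2 gives "Generalized Anxiety Disorder-7, Overall Anxiety Severity & Impairment Scale; Social Interaction Anxiety Scale".
- For depression, section 4.2 gives "Patient Health Questionnaire-9, Overall Depression Severity & Impairment Scale".
- For body image, section 4.2.2 lists the MBSRQ Appearance Evaluation subscale and "Body Appreciation Scale-2 – 10-items assessing the level of acceptance people have for their bodies". The visit table (11.1) places psychosocial measures under the secondary measures at all three assessments.
- Section 3.3 makes symptoms of depression and anxiety part of the secondary objectives.
- On timing, section 9.6 says "Data collection for the study will end by November 30, 2022".

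**SAP**

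- In section 4.2 the whole anxiety entry is "Anxiety symptoms* – Generalized Anxiety Disorder-7 (4- and 8-mo".
- Section 4.3 moves ODSIS and OASIS to exploratory, together with "Self-esteem* – Rosenberg Self-Esteem Scale (4- and 8-mo".
- Section 8.6 analyses those three scales at both follow-ups by the approach of 8.4.2.1.
- The summary is headed "STUDY SUMMARY (revised 1.24.23".

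**The concern.** A protocol secondary that is scheduled at every assessment and then disappears from the analysis plan raises the question of whether the result influenced the choice. The question is harder to answer here because the SAP's only visible date falls after the data were due to be complete and inside the analysis period that Protocol 4.1 starts in December 2022.

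SIAS matters most. It is the trial's only social-anxiety measure and belongs to a named secondary objective. Protocol 2.1 also links anxiety to poor condom-use communication, citing among other work a study of social anxiety as a risk factor for unprotected intercourse.

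The list of scales carries weight in this SAP. Section 6.3 rests interpretation of the secondary outcomes mainly on effect sizes, and the Bonferroni sentence in 8.4.1 and 8.4.2.1 is worded for sets of moderators, not for outcomes. Which scales appear therefore shapes the overall picture directly.

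**Working it through.** There is no stated figure to reproduce. The check compares the two outcome lists and the dates.

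**Step 1: the protocol's secondary instruments (4.2 and 4.2.2).** Counting the HIV/syphilis kit as one gives 21: mental health 8, minority stress 4, universal mechanisms 4, psychosocial 4, testing kit 1. Sum: 8 + 4 + 4 + 4 + 1 = 21.

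**Step 2: where each stands in the SAP (Study Summary, Table 1, 4.2, 4.3, 8.4, 8.6).**

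| SAP status | Number | Instruments |
|---|---|---|
| Still secondary | 13 | PHQ-9, GAD-7, SIDAS, AUDIT, DUDIT, three LGBIS minority-stress subscales, DERS, MSPSS, LGBIS family support, RRS, testing kit |
| Moved to exploratory | 3 | ODSIS, OASIS, Rosenberg |
| Absent | 5 | SIAS, MBSRQ Appearance Evaluation, Body Appreciation Scale-2, ACEs interview, COVID-19 questionnaire |

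Check: 13 + 3 + 5 = 21. The ACEs and COVID-19 instruments record exposure or context, so it is reasonable to set them aside. That leaves 5 − 2 = 3 absent outcome scales.

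**Step 3: size.** 3 absent scales × 2 follow-ups = 6 contrasts with no planned analysis, of which 2 are SIAS and 4 body image. Secondary anxiety scales fall from 3 to 1, but OASIS is still analysed, so analysed anxiety scales fall from 3 to 2.

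**Step 4: dates.** From 30 November 2022 to 24 January 2023 is 31 + 24 = 55 days.

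**Step 5: search for a reason.** The protocol revision history mentions a COVID-19 questionnaire and a revised ACEs instrument but no change to these six scales. The body of the SAP has no change log. SAP 6.3 refers to the number of secondary outcomes, but only to explain how results will be interpreted, not why scales were removed or moved.

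**The case against.** **Body image was never firmly in the analysis plan.** The two scales sit in a group called psychosocial variables, beside the ACEs and COVID-19 instruments, while neighbouring groups are called outcomes. Protocol 7.2.1 describes the secondary outcomes to be modelled as depression, anxiety and minority stress variables, and no objective or hypothesis mentions body image. This stands, and it makes the body-image omission the weaker part of the point. It does not remove it: 4.2.2 and the visit table still class the scales as secondary, and the SAP keeps other scales that 7.2.1 does not name, such as rumination and alcohol use.

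**The three moved scales are not lost.** This stands in full. SAP 8.6 analyses them at both follow-ups by the same method, so a reader can set GAD-7 beside OASIS. The change is one of label.

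**The retained scales look like natural leads.** PHQ-9 and GAD-7 come first in their domains and have existing Chinese versions, whereas ODSIS and OASIS were to be newly translated, and the same split is applied to depression and anxiety. This is plausible, but the SAP does not say it. Nor would it explain SIAS, which Protocol 4.2.2 also gives in an existing Chinese version.

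**The date proves little.** This stands. It marks a revision without saying what changed, and 30 November 2022 is only a planned date. The protocol foresaw review of risk data by condition by the monitoring board (7.2.3), and SAP 7.1 lists efficacy among the monitoring topics. Neither shows that the SAP's authors had seen results by arm.

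**Conclusion.** The point holds as an unexplained discrepancy. Three protocol secondary scales, or six contrasts, have no place in the SAP, and three others are relabelled exploratory without a reason. The exposure to a charge of selective reporting is clearest for SIAS, smaller for body image, and slight for ODSIS, OASIS and Rosenberg.

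A reader might go further in three ways that the documents do not support:

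- **That GAD-7 was kept because it gave the best result.** Nothing shows when the outcome list was changed or who had seen data by arm.
- **That the missing results will be suppressed.** The SAP does not forbid reporting them, and the protocol still lists them. What is true is that the SAP contains no commitment to analyse them.
- **That a best-of-three false-positive rate applies.** Such a rate assumes three independent anxiety scales with only the best kept. OASIS is still analysed, anxiety scales are likely to correlate, and SAP 6.3 does not rest interpretation on significance.

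The conclusion assumes that the scales were collected as scheduled and that no separate document explains the changes.

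**What to change.** 1. Add SIAS to SAP 4.2, Table 1 and 8.4.2.1 as a secondary outcome at 4 and 8 months, with the same model.
2. Add MBSRQ Appearance Evaluation and the Body Appreciation Scale-2 as secondary or, at least, to SAP 4.3 and 8.6 as exploratory.
3. Commit to reporting all three whatever the result.
4. Leave ODSIS, OASIS and Rosenberg exploratory.
5. Add a dated table of outcome changes from protocol to SAP. For each change it should give the reason and state truthfully whether the change was made before access to results by arm. If it was made after, the table should say so.

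The cost is SAP wording, six more contrasts on data the protocol already schedules, and a longer results table. As the Bonferroni sentence is worded, no threshold for an outcome changes. If it were applied to mental-health outcomes as a set, SIAS would raise that set from 5 scales to 6, and the per-scale level would go from 0.05/5 = 0.0100 to 0.05/6 = 0.0083.

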4.3 Exploratory Outcomes

- *Depression severity and impairment* -- Overall Depression Severity and Impairment Scale (4- and 8-mo)
- *Anxiety severity and impairment* – Overall Anxiety Severity and Impairment Scale (4- and 8-mo)
- *Self-esteem* – Rosenberg Self-Esteem Scale (4- and 8-mo)

5. RANDOMIZATION

5.1 Method of Randomization

Randomization occurred on the participant level. Participants were randomly assigned to receive one of two conditions: iCBT ESTEEM or self-monitoring (N = 120). We used a 1:1 randomization scheme such that for every one participant randomized to iCBT ESTEEM, one participant was randomized to self-monitoring. Participant randomization was stratified based on mental health (i.e., eligible based on depressive symptoms, anxiety symptoms, or both based on the Brief Symptom Inventory-4). Stratified randomization occurred using a random number table generated by SPSS such that 60 participants were randomized to each condition.

5.2 Allocation Concealment

Concealment was not employed given that all measures involved self-report or objective HIV/STI test results.

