5.5 Consent/Accent Procedures/HIPAA Authorization

Comprehension test. A waiver of documentation of consent is planned for the all portions of this comprehension test study (see attachments on IRES for the online screener). For the comprehension test, potential participants will take the online screener for the study via the secure CSU Sojump survey software. As previously noted, the only inclusion criteria for the comprehension test will be: 16-30 years old, live in Hunan province China, current gender identity as male, report past 12-month sex with men, weekly access to internet on a laptop, desktop, or tablet device, ability to read, write, and speak in Mandarin, and provision of informed consent (see Section 5.3 for inclusion criteria for the full study). An RA at CSU will schedule a WeChat call with 10 YMSM participants who express interest in participating in the comprehension test. Prior to the WeChat call, the CSU RA will send a copy of the consent form via WeChat to the participant and ask them to review the form before the WeChat call. During the WeChat call, the CSU RA will read through the consent form and answer any questions from the participants. Participants will be informed on the consent form that they will receive 200RMB for reviewing the 10 iCBT session modules and 50RMB for participating in a follow-up interview. Any ineligible participants will be informed at the end of the online screener of their ineligibility for the study.

RCT. For the full RCT study (Aim 2), consent will be obtained at three time points. A waiver of documentation of consent is planned for all portions of this study:

First, participants will complete an initial online screener via the secure CSU Sojump survey software (see attachments on IRES for the online screener).

Second, if participants are eligible for the study based on the online screen, a CSU RA will schedule a video screen via WeChat for further assessment. At the beginning of this video call, participants will provide verbal consent before continuing with the video screen (see the Measure Packet uploaded on IRES for the script that will be followed for the video screener). Ineligible participants will be informed at the end of the video screener of their ineligibility for the study. If participants are eligible following the video screener, an at home HIV/STI testing kit will be sent to the participant via mail within 2 days of the video screener.

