Appropriate risk-reduction counseling will be provided to all participants on the same day of testing. Enclosed within testing kits, all participants will receive lubricant and condoms. The rapid test results for both HIV and syphilis will be ready to be read by participants in 20 minutes. HIV/STI test results will be discussed with participants by study counselors. Like conventional HIV enzyme immunoassays (EIAs), rapid HIV/STI tests are screening (i.e., not diagnostic) tests that require diagnostic confirmation by Western Blots if reactive (positive). Participants who test preliminarily positive (or have inconclusive tests) will be immediately linked to Zuo An Cai Hong for confirmatory testing, care, and treatment. Counselors will offer to make an appointment for participants at a local Zuo An Cai Hong, which has 7 offices across Hunan province. Participants testing HIV positive will not be randomized into the study, as HIV negative status is one of the inclusion criteria, so they will receive immediate HIV/STI counseling by one of our counselors, followed by medical attention by Zuo An Cai Hong to which they will be promptly linked. Participants who test negative will be given the option of continuing to move forward with the research study.

Participants who continue to express interest in the study will be sent a copy of the consent form via WeChat. Participants will be asked to read the consent form on their own. CSU RAs will schedule a consent call with participants via WeChat to read over the consent form with them, as well as check their understanding of the consent form via asking questions about the content of the study and ability for participants to withdraw from the study at any time. After participants provide verbal consent, we will assign them a username and password for the Karolinska Institutet's secure iCBT online platform that houses the ESTEEM iCBT treatment and self-monitoring weekly assessment for both conditions. Participants will be required to login to the Karolinska Institutet's secure iCBT platform before they are sent the baseline assessments. Upon signing into the iCBT online platform, a CSU RA will send a hyperlink to the participant via WeChat to complete the baseline surveys on Sojump. After completion of the baseline completion, a CSU RA will schedule a final WeChat call with each participant for their randomization into either the ESTEEM iCBT or self-monitoring condition.

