6.2 Method of Assignment/Randomization (if applicable)

Participants who are confirmed eligible via the study screeners and who test negative for HIV based on the at home HIV/STI testing kit will then be randomized to ESTEEM iCBT or the weekly self-monitoring condition. Participant randomization will be stratified based on mental health (i.e., eligible based on depressive symptoms, anxiety symptoms, or both on the Brief Symptoms Inventory-4). Randomization will occur via use of a random number table generated by SPSS, which has been used reliably by [name] and her team successfully when implementing stratified randomization for previous studies.

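### SAP 5.2 says allocation was not concealed and gives a reason that belongs to masking; neither document says who held the list or who could see the next assignment

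*SAP*

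**What the plan says.** SAP 5.2, headed Allocation Concealment, consists of one statement: "Concealment was not employed given that all measures involved self-report or objective HIV/STI test results".

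SAP 5.1 describes the sequence. On the ratio: "We used a 1:1 randomization scheme such that for every one participant randomized to iCBT ESTEEM, one participant was randomized to self-monitoring". On method and arm sizes: "Stratified randomization occurred using a random number table generated by SPSS such that 60 participants were randomized to each condition". The strata are the three ways of qualifying on the Brief Symptom Inventory-4 (BSI-4): depression, anxiety or both. Protocol 6.2 agrees: "Randomization will occur via use of a random number table generated by SPSS". It adds that the site team has used such tables in previous studies.

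On who deals with participants before assignment, Protocol 5.5 says that "a CSU RA will schedule a video screen via WeChat for further assessment". Protocol 6.1 has site research assistants hold the consent call. After the baseline survey, "a CSU RA will schedule a final WeChat call with each participant for their randomization".

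On adjustment, Protocol 7.2 models CAS at 4 and 8 months with baseline CAS as an adjustment variable. SAP 8.3 models change in CAS from baseline to 8 months through condition-by-time contrasts, and lists as covariates only those baseline variables found unbalanced. SAP 8.2 describes the balance check in terms of demographic characteristics.

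**The concern.** Concealment and masking protect against different things. Concealment keeps whoever screens, consents or schedules a participant from knowing which arm comes next. It acts before assignment. Masking acts afterwards, on treatment and outcome assessment. An outcome measured by questionnaire or rapid test says nothing about whether the next line of the list was visible during recruitment.

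If it was visible, a participant could be encouraged, delayed or let go according to the arm that was due. The arms could then differ in risk behaviour or motivation from the start. Analysing everyone as randomized does not remove that difference, and covariate adjustment removes only the part carried by measured variables. The claim at stake is that the arms are comparable except for chance and treatment.

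**Working it through.** The documents give no figure on this point to reproduce, so the check is mainly a comparison of passages.

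**1. Does the reason fit the statement?** The statement concerns concealment; the reason concerns outcome measurement. There are two readings:
- The authors meant masking. Then 5.2 is mislabelled and the documents say nothing about concealment. The reason is also weak as a masking argument, because self-report comes from participants who know whether they have a therapist and modules or only a weekly survey.
- The authors meant concealment. Then the list was open, and the reason does not justify it.

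Either way 5.2 needs correcting.

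**2. Does another section fill the gap?** SAP 5.1 and Protocol 6.2 give the source of the sequence, the strata and the ratio. Neither gives who generated the list for this trial, who held it, how an assignment was released, or any block size. Protocol 6.1 names who schedules the randomization call, not who holds the table.

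**3. Was the sequence restricted?** SAP 5.1 says the table was used so as to give 60 per arm. Unrestricted 1:1 assignment of 120 people gives exactly 60:60 with probability C(120,60)/2^120 ≈ √(2/(π × 120)) = 0.073, about 7%. The wording therefore points to some restriction, but its form is not given.

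**4. Why the form matters.** Block sizes here are assumptions. Suppose the list is hidden but past assignments within a stratum are known, and one always guesses the arm with more places left. The share of correct guesses is the mean of max(a, b)/(a + b) over the sequence, where a and b are the places left in each arm. For blocks of 4 this is (1/2 + 2/3 + 2/3 + 1)/4 = 70.8%.

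| Assumed scheme | Correct guesses |
|---|---|
| Blocks of 4 | 70.8% |
| Blocks of 8 | 66.6% |
| One unstratified 60:60 list | 55.3% |
| List visible | 100% |

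The documents do not say which row applies. That is why custody and blocking both need stating.

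**5. What does the analysis already protect?** Baseline CAS is handled in Protocol 7.2 as a covariate and in SAP 8.3 through change from baseline. The BSI-4 stratum balances the design but is named in neither model. In the SAP, further adjustment depends on observed imbalance: 8.2 says it will be considered and 8.3 lists it, with no rule for what counts as imbalance.

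**The case against.** The strongest reply is that this is a labelling slip. The reason given makes sense only for masking, so 5.2 may be a misplaced remark about outcome assessors and not an admission that recruiters saw the list. Protocol 6.1 puts the video screen, home HIV test, consent and baseline survey before the randomization call, and eligibility rests largely on self-report and a test kit. Baseline CAS is already in the analysis.

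Much of this stands. It lowers the risk and rules out treating an open list as fact. It does not repair 5.2, because no other section describes concealment. Some discretion also remains: the judgement-based exclusions in Protocol 5.3, encouragement at consent, and the timing of the final call. The protection from ordering holds only if staff could not see the next assignment before that call. Protocol Table 1 also lists the randomization call in a column before the baseline surveys. Column order need not be time order, but the sequence is worth confirming.

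Stronger readings that a reader might infer, and that the documents do not support:
- **Assignment in pairs, with half of all assignments certain.** The phrase "for every one participant randomized to iCBT ESTEEM, one participant was randomized to self-monitoring" explains the 1:1 ratio in its own sentence. No block size is given anywhere.
- **A bias equal to a stated fraction of the d = .40 design effect.** That needs a between-arm shift in prognosis, and the documents offer no basis for one. Baseline adjustment would also absorb some of any shift carried by baseline CAS.
- **No protection beyond adjusting for unbalanced demographics.** Protocol 7.2 and SAP 8.3 both take baseline CAS into account, and the covariate wording in SAP 8.3 is not confined to demographics.

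**Conclusion.** The point holds as a defect in SAP 5.2 and a gap in both documents. The plan states that concealment was not used, supports this with a reason that does not bear on it, and does not say who held the SPSS list or who could see the next assignment. Selection before randomization is possible and undemonstrated.

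No size of bias can be given. The guess rates describe predictability under assumed block sizes, and a predictable sequence does no harm unless someone acts on it. The conclusion rests on the text of SAP 5.1 and 5.2 and Protocol 6.1 and 6.2, and assumes that no other trial document describes custody of the list. If one does, the point reduces to correcting the wording of 5.2 and improving the covariate rule in 8.3.

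**What to change.** The SAP (revised 1.24.23) reports randomization in the past tense, so a new allocation procedure cannot help this trial. Two SAP changes can.

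**SAP 5.2.** Treat concealment and masking separately. State who generated the list, who held it, any blocking within the BSI-4 strata, who could see the next assignment and when, and whether release always followed the baseline survey. If the list was open to staff who screened, consented or scheduled, say so and carry it into the report as a limitation.

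**SAP 8.3.** Replace adjustment only for covariates found unbalanced with prespecified adjustment for the BSI-4 randomization stratum and baseline CAS, whatever the observed balance. Baseline CAS can enter as a covariate, as in Protocol 7.2, or through the baseline response in the repeated-measures model. The SAP should say which, because using the same value in both roles would require restructuring the model. Baseline PHQ-9 and GAD-7 are optional. Protocol 4.1 has analysis starting in December 2022, so date the change; if outcomes by arm have already been seen, also report the model as now written.

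The cost is a few sentences, one stratum term and baseline data already collected. The drawback is that the SAP may have to record a limitation, and adjustment cannot recover unmeasured differences such as motivation.
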